After discharge the subject will continue to be closely followed for evidence of adverse events, with outpatient follow-up evaluations scheduled at Day 10 and Months 1, 2, 3, 4, 5, 6, 9 and 12, or more often if

medically indicated. HSV detection will be performed at additional time points. The visits at months 2, 4 and 5 will consist of sample collections and a study coordinator visit only. Due to the complicated procedure for obtaining samples remotely at visits 2, 4 and 5, if a patient is unable to travel then, and if determined feasible by the PI, an attempt can be made to have the specimens collected by the patients' referring physician and sent to UAB for analysis.

The safety evaluation schedule is outlined in detail below in Section 8. Per FDA guidelines, subjects will be followed for survival. This will be achieved with monthly phone calls to subject. Additionally, when possible, subjects will be followed for emergence of any chronic or acute conditions that might be attributed to the study agent for up to 15 years during clinical visits with their standard of care practitioner.

Most adverse events will be managed according to standard conventions. General or specific neurologic worsening observed in the first several days after M032 administration could be due to edema, hydrocephalus, hematoma, or encephalitis. Such problems occurring later may also be attributable to tumor progression. When appropriate, an MRI will be done to help determine the cause of the neurologic changes.

- Cerebral edema/hydrocephalus: This commonly occurs in tumor patients post-operatively, and usually responds to standard measures for the treatment of increased intracranial pressure.
- Hematoma: PT, PTT, and platelet count will be obtained. A small hematoma may simply be watched and the patient treated as above for edema and then rescanned to exclude an enlarging lesion. A large hematoma or one associated with progressive neurologic deterioration may require operative evacuation.

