Day 0 (biopsy and catheter placement)

- Admit to the hospital for biopsy surgery and if eligible, catheter placement
- Review medications
- AE monitoring
- Obtain vital signs (pulse, blood pressure, respiratory rate, temperature and weight) prior to surgery
- Perform a neurological (nervous system) examination to include assessment of cranial nerve abnormalities, gait abnormalities (when appropriate), sensory abnormalities, muscle strength, and level of consciousness
- Obtain a stereotactic MRI to determine site for the biopsy and catheter placement
- Perform the biopsy and, if eligibility criteria are met, place and label up to 4 catheters

- Prime each catheter with 0.4 ml sterile saline solution and cap the catheters
- Admit to the Neurosurgery Intensive Care Unit for routine post-biopsy care and observation
- Obtain CT scan to ensure the catheters are in the proper position. (May be completed on Day 1 prior to drug administration)
- Collect blood for the following:
 - Immune studies - to be stored for future research – collect post-op
- Should a patient have an access device (eg., Rickham or Ommaya reservoir) that accesses either the more central portion of the tumor/cyst, or the CSF space, fluid will be aspirated as possible (expected, 2-10cc) from the catheter for laboratory studies. These specimens will be obtained at either the pre op clinic visit or the day of surgery, as well as up to daily during the inpatient hospitalization (per the surgeon's discretion), and again at post op visit day 10, Day 28, and Months 3,6,9 and 12

Day 1 (drug administration):

- If subject's condition is stable, transfer to a Clinical Research Unit inpatient bed for drug infusion and monitoring
- Review medications
- Perform a complete physical exam including wound assessment
- If not completed on Day 0, obtain a CT scan to ensure the catheters did not move and are still in the proper place
- Obtain pathology report and verify diagnosis

- Administration of study drug which will take approximately 6 hours (may last up to 12 hours)
- Study Drug Administration
 - Acquisition of study drug and diluent
 - Store syringes in refrigerator (4° C) until needed
 - Flush infusion tubing with diluent provided by pharmacy
 - Connect syringe with study drug to infusion tubing
 - Prime with 4.6 ml of the diluted virus preparation making sure that any excess study drug is disposed according to Biosafety Level 2 procedure
 - Connect tubing to catheter

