9.3 Response Criteria

The following criteria are based upon the volume changes that correspond to the definitions proposed by the MacDonald criteria. For the purposes of this study, the objective response of each patient's disease to M032 will be evaluated by the comparison of a baseline MRI scan to follow-up MRI. For those patients receiving intratumoral inoculation, the screening MRI will serve as the baseline MRI, and follow-up scans will be done at study Day 3, Day 28, Month 3, Month 6, Month 9 and Month 12. To prevent the introduction of observer bias, a software package which determines tumor areas and volumetrics via assessment of pixel intensity will be utilized to compare pre-and post-treatment images.

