9.3.1 Evaluation of Target Lesions

“Response” is defined as follows:

Complete Response (CR) - Disappearance of all treated enhancing tumor on MRI scan, off steroids, and neurologically stable or improved.

Partial Response (PR) - greater than 50% reduction in the treated enhancing tumor on MRI scan, stable or reduced steroid dose, and neurologically stable or improved.

Progressive Disease (PD) - greater than 25 % increase in the treated enhancing tumor on MRI scan, stable or increased steroid dose, and neurologically stable or worse.

Stable Disease (SD) - all other situations

Some patients on this trial may be taking dexamethasone and/or bevacizumab. Those who have decreased the dose of one of these medications to one lower than that utilized at the time of the previous MRI AND this dose decrease has occurred within two weeks of the MRI shall not be determined to have progressed even if the MRI meets the criteria for PD above, but rather that MRI shall be considered non-evaluable for response. Similarly, should an increase in steroid dosage or bevacizumab dosage occur within two weeks of an MRI compared to the prior MRI, the patient will not be eligible for consideration of a CR or PR but instead that MRI will be considered non-evaluable.

Note that since this is considered an immunotherapy trial, the appearance of lesion(s) does not necessarily indicate PD.

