9.3.4 Pseudoprogression

Pseudoprogression is a well-known entity in oncolytic viral therapy of glioma. Currently, the immunotherapy Response Assessment in Neuro-Oncology (iRANO) group is proposing criteria for determination of pseudoprogression in immunotherapy trials which are not yet published. [40] We will utilize the following criteria to address this phenomenon in this trial : If tumor appears to enlarge or demonstrates increased enhancement by MRI consistent with PD, patients will undergo repeat imaging and clinical assessments at 3 months to determine whether the changes demonstrate true progression or pseudoprogression. Note that the investigator may obtain an MRI prior to this 3 month interval as indicated. Should significant neurologic deterioration occur that cannot be ascribed to tumor or pseudoprogression related events such as seizures or medication changes (e.g., steroid tapers) the patient will be considered to have progressed. During the interval, the patient may be watched or treated with bevacizumab and/or dexamethasone at the discretion of the investigators. If the patient improves with bevacizumab (to be used

preferentially at a suggested dose of 10mg/kg IV, every two weeks, for three months; previous tumor progression on bevacizumab does not preclude its use herein) and/or additional steroid administration (to be used if bevacizumab is contraindicated or insufficient) and the MRI changes in lesion size/and or enhancement also improves, the patient will be determined to have not progressed but to have suffered pseudoprogression, and will continue follow-up within the trial under the previously defined schedule. Should neurologic symptoms and/or imaging changes progress despite steroid administration on follow-up imaging, the patient will be determined to have progressed and the date of progression shall be assigned to the date of the initial scan that demonstrated findings consistent with PD as defined above.

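### The Day 3 MRI counts as a response scan, so progression confirmed later can be dated back to three days after surgery and two days after infusion

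*Combined protocol and SAP*

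**What the plan says.** - **Which scans count.** Under 9.3, "follow-up scans will be done at study Day 3, Day 28, Month 3, Month 6, Month 9 and Month 12". Response is "evaluated by the comparison of a baseline MRI scan to follow-up MRI", and the comparison scan predates surgery: "the screening MRI will serve as the baseline MRI". No sentence limits Day 3 to safety.
- **Timing.** Section 8.1 labels the first two study days "Day 0 (biopsy and catheter placement" and "Day 1 (drug administration". Catheters come out 6 to 18 hours after the infusion ends (4.1). The Day 3 MRI is taken before discharge (8.1).
- **What PD is.** Section 9.3.1 requires "greater than 25 % increase in the treated enhancing tumor on MRI scan, stable or increased steroid dose, and neurologically stable or worse".
- **How PD is confirmed and dated.** Under 9.3.4, apparent PD leads to reassessment at 3 months, with earlier MRI allowed. If the patient and the images improve, it is pseudoprogression and follow-up continues. If symptoms or images progress, "the date of progression shall be assigned to the date of the initial scan that demonstrated findings consistent with PD as defined above".
- **What PFS is.** Section 1.3 makes it a secondary objective. Section 9.5 says it will be reported but gives no time origin, event definition or censoring rule. The nearest guide is 9.4.3, which counts stable disease from the start of treatment.

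**The concern.** By Day 3 the lesion has been biopsied, has held one to four catheters, has been infused and has had the catheters withdrawn, yet it is compared with a scan taken before any of this. The protocol expects disturbance in this period: "General or specific neurologic worsening observed in the first several days after M032 administration could be due to edema, hydrocephalus, hematoma, or encephalitis" (5.1). That sentence is about clinical worsening, not enhancing volume, but it names processes that also bear on an early scan.

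The PD rule does not filter such change out. It is met with stable or worse neurology and with a stable or increased steroid dose, all compatible with a post-operative state. Size comes from software based on pixel intensity (9.3), and no step for separating surgical change from tumor is described.

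At stake is the date of progression. A patient whose disease does progress later may have that event placed at Day 3 because of change that reflects the procedure. PFS is then shortened by the scan schedule and the dating rule, and in a trial of 8 to 24 patients a few such dates can move a median.

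**Working it through.** The documents state no PFS figure to reproduce, so the check is on dates and on the size of the threshold.

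**Intervals** (study days from 8 and 8.1; month taken as 30.4375 days)
- Surgery to Day 3 scan: 3 − 0 = 3 days.
- Infusion to Day 3 scan: 3 − 1 = 2 days.
- Infusion to Day 28 scan: 28 − 1 = 27 days; the ±4-day window gives 23 to 31.
- Infusion to Month 3 scan: 3 × 30.4375 − 1 = 90 days.

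**Following the rules for a patient with a rise above 25% on Day 3**

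| Later course | Date under 9.3.4 | PFS from infusion | PFS if Day 3 cannot count |
|---|---|---|---|
| Improves | Pseudoprogression, no event | unaffected | unaffected |
| Day 28 also meets PD, progression confirmed | Day 3 | 2 days | 27 days |
| Day 28 below threshold, Month 3 meets PD, progression confirmed | Not stated: Day 3 or Month 3 | 2 or about 90 days | about 90 days |

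The shift is 27 − 2 = 25 days in the second row and up to 90 − 2 = 88 days in the third. Counting PFS from Day 0 adds one day to every entry and leaves the shifts unchanged.

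**How small a 25% rise is** (spherical lesion; eligible diameter 1.0 to 5.5 cm, section 3.1.7)
- Read as volume: 1.25^(1/3) − 1 = 7.7% in diameter. For 20 mm: 20 × 0.077 = 1.5 mm.
- Read as area: 1.25^(1/2) − 1 = 11.8% in diameter. For 20 mm: 20 × 0.118 = 2.4 mm.

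**What it could do to a median.** This is an illustration on assumptions, not an estimate. It takes 24 patients, exponential progression times, progression recorded at the next scan from Day 28 on, and no loss before 12 months. A share of patients has a Day 3 rise, and all of them who progress within 12 months are dated to 2 days. This is the upper end, because it treats Day 3 as the initial scan whatever Day 28 shows. Entries are average median PFS in days.

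| Assumed true median | 0% share | 10% | 20% | 30% | 50% |
|---|---|---|---|---|---|
| 60 | 96 | 90 | 79 | 63 | 22 |
| 90 | 136 | 120 | 105 | 86 | 36 |
| 180 | 231 | 217 | 201 | 181 | 122 |

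The 0% column exceeds the true median because progression is only seen at scheduled scans.

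**The case against.** The best defence is 9.3.4 itself. A Day 3 rise only triggers reassessment. Change that resolves is pseudoprogression, and backdating needs later progression, most naturally of the same changes. A reader might infer that surgical change alone can produce a progression event at two days. The text does not support that, and this part of the defence stands. It protects only patients who improve, however, and leaves the date exposed in those who go on to progress.

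The scheduled Day 28 MRI also matters. A reader might take 2 days against about 90 as the standard error. Where Day 28 also meets PD the error is about 25 days. Where Day 28 is back below threshold, it is unsettled whether Day 3 remains the initial scan. The large figure is one reading of an ambiguous rule.

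Section 9.3.1 calls an MRI non-evaluable when steroid or bevacizumab was increased within the preceding two weeks. That sentence is framed around complete and partial response, while the PD definition expressly accepts an increased steroid dose. Even read broadly, it leaves out patients on a stable dose.

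Three further inferences go beyond the documents:
- That a falsely low Day 3 reading will commonly become the smallest-measurement reference. The mechanism here is enlargement, which points the other way.
- That the 2.4 ml infused can be set against 25% of lesion volume. Infused fluid is not enhancing tumor.
- That M032 cannot affect the image by Day 3, or that the software cannot separate blood from tumor. Both are plausible, but neither is stated.

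Finally, PFS is descriptive and 11.4 plans no test or dose comparison of it. That stands, and it limits the weight of the point.

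**Conclusion.** The dating flaw holds. Following 9.3, 9.3.1 and 9.3.4 as written, progression confirmed later can be dated to a scan taken three days after surgery and two days after infusion. If PFS runs from infusion, an assumption because 9.5 gives no origin, that patient's PFS is 2 days. It would be about 27 days if Day 28 also meets PD. It would be about 90 days if Month 3 is the next PD scan, and there the text does not settle which scan is the initial one.

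The documents give no share of patients affected, so no count of altered PFS times can be claimed. The medians tabulated above show direction and sensitivity only.

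The consequence is limited to a descriptive secondary endpoint. The toxicity-based primary endpoint and the dose-finding are untouched. The one link to a decision is in 4.1.1, where PFS or survival may inform the phase II dose if no MTD is reached. This is an inexpensive correction worth making, not a threat to the trial.

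**What to change.** State in 9.3 that the Day 3 MRI is kept as a safety and post-operative scan and is not used to assign complete response, partial response, stable disease or PD. State in 9.3.4 that it cannot be the initial scan for dating progression. Day 28 then becomes the first scheduled response scan. For consistency, exclude Day 3 from the smallest-measurement reference in 9.3.3, 9.4.2 and 9.4.3.

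Two related clarifications would complete it. Section 9.3.4 should say which scan is initial when an intervening scan falls back below the PD threshold. Section 9.5 should give the PFS origin, event and censoring rules.

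No procedure is added or removed. The cost is small: genuine imaging progression in the first days would be dated at Day 28 at the earliest on scheduled scans, although neurologic deterioration can still be called progression under 9.3.4.

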9.3.1 Evaluation of Target Lesions

“Response” is defined as follows:

Complete Response (CR) - Disappearance of all treated enhancing tumor on MRI scan, off steroids, and neurologically stable or improved.

Partial Response (PR) - greater than 50% reduction in the treated enhancing tumor on MRI scan, stable or reduced steroid dose, and neurologically stable or improved.

Progressive Disease (PD) - greater than 25 % increase in the treated enhancing tumor on MRI scan, stable or increased steroid dose, and neurologically stable or worse.

Stable Disease (SD) - all other situations

Some patients on this trial may be taking dexamethasone and/or bevacizumab. Those who have decreased the dose of one of these medications to one lower than that utilized at the time of the previous MRI AND this dose decrease has occurred within two weeks of the MRI shall not be determined to have progressed even if the MRI meets the criteria for PD above, but rather that MRI shall be considered non-evaluable for response. Similarly, should an increase in steroid dosage or bevacizumab dosage occur within two weeks of an MRI compared to the prior MRI, the patient will not be eligible for consideration of a CR or PR but instead that MRI will be considered non-evaluable.

Note that since this is considered an immunotherapy trial, the appearance of lesion(s) does not necessarily indicate PD.

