4.3 Supportive Care Guidelines

Appropriate supportive care during the duration of the study includes the following:

- Bevacizumab or steroid administration for neurologic symptoms arising from increased edema or intracranial pressure, which are presumed mechanisms of action for M032, will be allowed, if deemed appropriate and safe in the determination of the investigator. The increase in steroid dose will be kept to a minimum as patient neurologic condition permits. In general, UAB Neuro-oncology protocol is that Avastin is given every two weeks at a dose of 10/kg mg IV. Dosage adjustments or cessation of drug

may be made should adverse events (Uncontrolled hypertension, proteinuria, bleeding, thrombosis, etc.) occur and are made on a case-by-case basis by the prescribing neuro-oncologist.

- Proton pump inhibitors or H2 antagonists for control of steroid-induced gastric irritation
- Anti-epileptic medicines for control of partial or generalized seizures
- Post-operative neurological intensive care that is routine for the neurosurgical interventions involved in the administration of M032
- Other than a restriction on medications with anti-HSV activity (to be given only for the management of an adverse event), there are not any limitations on concomitant medications that patients may receive for other co-morbidities

Management of adverse events is discussed in **Section 5**.

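### Section 9.3.1 does not say what a stable steroid dose is compared with, so tumor growth after an older dexamethasone decrease can be coded SD rather than PD

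*Combined protocol and SAP*

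**What the plan says.** Section 9.3.1 makes PD depend on three conditions together: "greater than 25 % increase in the treated enhancing tumor on MRI scan, stable or increased steroid dose, and neurologically stable or worse". The residual category is "Stable Disease (SD) - all other situations".

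An exception follows for dexamethasone and bevacizumab. It applies to patients who have "decreased the dose of one of these medications to one lower than that utilized at the time of the previous MRI", and it adds a timing condition: those for whom "this dose decrease has occurred within two weeks of the MRI shall not be determined to have progressed even if the MRI meets the criteria". Such a scan is non-evaluable. A mirror rule bars CR and PR after a recent dose increase.

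Section 9.3.4 (Pseudoprogression) sets the dating rule. If worsening continues despite steroids, "the date of progression shall be assigned to the date of the initial scan that demonstrated findings consistent with PD as defined above". It also allows an MRI before the three-month recheck, and counts certain neurologic deterioration as progression.

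Sections 9.3.3 and 9.4 measure progression from the smallest tumor measurement since treatment started. Section 9.3 fixes the imaging: "follow-up scans will be done at study Day 3, Day 28, Month 3, Month 6, Month 9 and Month 12".

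**The concern.** The PD line needs a steroid comparator (previous MRI, baseline, or a recent period) and gives none. PR lists a reduced dose among its permitted steroid states; PD does not. On a literal reading, a scan with growth above 25% and a reduced dose therefore fails PD. Unless the reduction was recent enough for the exception, the scan drops into SD.

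That ordering is backwards. A recent decrease, which confounds the image most, gives a non-evaluable scan. An older decrease, which confounds it less, gives the more favorable label. The section sets no minimum size of decrease and no ceiling on growth. A Month 3 scan coded this way could also help meet the 12-week SD requirement in Section 9.4.1.

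The outputs at stake are time to progression and PFS (Synopsis, Sections 1.3 and 9.5) and the SD and PD percentages by cohort (Section 11.4.2). Two other sections also use them. Section 4.1.1 lets PFS or OS inform the phase II dose if no MTD is reached. Section 4.4 ties the efficacy schedule and the acceptability of other treatments to Section 9 progression.

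**Working it through.** The plan gives no figure to reproduce here, so the check applies the rules to a test scan and then measures the scan intervals.

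**Step 1: classification.** Take a scan with 30% growth in a patient who is neurologically stable or worse, with dexamethasone lower than at the previous MRI. Only the timing of the decrease varies.

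| Days from decrease to MRI | Stable = not below dose at previous MRI | Stable = unchanged for two weeks |
|---|---|---|
| 7 | non-evaluable | non-evaluable |
| 14 | non-evaluable | non-evaluable |
| 15 | SD | PD |
| 42 | SD | PD |
| 80 | SD | PD |

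The readings part at day 15, so two assessors following the text could code the same scan differently. A third comparator, the baseline dose, is not mentioned in the section. If it were used, PD could not be met while the dose stayed below baseline. Bevacizumab is absent from the PD line, so the SD route concerns steroids only.

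**Step 2: intervals.** Inputs are the scheduled MRIs in Section 9.3 and the visit windows in Section 8. The documents do not define a month, so I assume 28 to 30.4 days. Month 3 is then day 3 × 28 = 84 to 3 × 30.4 ≈ 91.

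- Exposed days = interval since the previous scheduled MRI − 14.
- Deferral = next scheduled MRI − current MRI.

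| Scan showing growth | Days since previous scheduled MRI | Exposed days | Deferral to next scheduled MRI |
|---|---|---|---|
| Day 28 | 28 − 3 = 25 | 11 (44%) | 56–63 days |
| Month 3 | 56–63 | 42–49 (75–78%) | 84–91 days |
| Months 6, 9 | 84–91 | 70–77 (83–85%) | 84–91 days |
| Month 12 | 84–91 | 70–77 (83–85%) | none scheduled |

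For growth on the Day 3 scan the deferral is 28 − 3 = 25 days. If the Day 0 MRI counts as the previous one, any decrease since then is necessarily within two weeks, so that scan would be non-evaluable rather than SD.

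With ±12-day windows at both ends, a three-month deferral spans 84 − 24 = 60 to 91 + 24 = 115 days. The percentages are shares of calendar time, not probabilities that a decrease occurs.

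**Step 3: does Section 9.3.4 recover the date?** Not clearly. Its dating clause points to a scan consistent with PD as already defined, and on the previous-MRI reading this scan did not meet that definition. The clause is also conditional on worsening while steroids are given, which fits poorly when they have been lowered.

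**Step 4: what holds on either reading.** A decrease within two weeks makes the scan non-evaluable. Section 9.3.1 then sets no dating rule for growth confirmed at the next scan.

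**The case against.** The strongest reply is that SD is not the only reading. The exception bars a finding of progression after a recent decrease even where the MRI meets the PD criteria. If every decrease since the previous MRI already failed PD, that bar would be redundant for dexamethasone. The capitalized conjunction joining its two conditions also suggests that only recent decreases were meant to block PD. The steroid eligibility criteria (3.1.11 and 3.2.7) use a two-week period too. On this view an older decrease leaves the dose stable, and the scan is PD without delay. This stands as a tenable reading, so the documents do not support saying that the rule systematically converts growth into SD. It does not settle the matter, because the bar can be read as referring to imaging criteria alone and the PD line never states a window.

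A reader might also infer that tapering is routine in this trial, so that most patients are exposed. The text does not say so. Section 4.3 states that "The increase in steroid dose will be kept to a minimum as patient neurologic condition permits", which limits increases and does not direct decreases. The low-dose target in the eligibility criteria applies at the time of treatment. Section 9.3.4 mentions tapers only as an example.

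Nor is a uniform three-month delay supported: it fits growth first seen at Months 3, 6 and 9 only. An earlier MRI or neurologic deterioration under Section 9.3.4, or a standard-of-care MRI captured at an unscheduled visit, can shorten it. Growth first seen at Month 12 may lose its PD label, but it is not unrecorded, because Section 11.4.2 analyzes all tumor volume changes with steroid use in view.

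Finally, PFS here is secondary and descriptive, with no test or event target. That limits the consequence but does not justify leaving a progression rule open to two codings.

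**Conclusion.** The point holds as an undefined comparator that, on one natural reading, gives a perverse classification. Read against the previous MRI, growth above 25% after a dexamethasone decrease more than two weeks old is SD. PD is then deferred by 25 days from Day 3, 56–63 days from Day 28, or 84–91 days from Months 3, 6 and 9, with no later scheduled scan after Month 12. Read as two-week stability, there is no such gap.

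The deferrals assume that growth persists, that the next scan is evaluable, and that no off-schedule MRI or neurologic route intervenes. On the previous-MRI reading the bias runs toward longer PFS and time to progression and a higher SD percentage. The DLT/MTD endpoint is not affected.

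It is tempting to convert this into a number of patients. The documents give no frequency of steroid decreases, so any such count would rest on an unsupported assumption.

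**What to change.** Amend Section 9.3.1; this is endpoint classification only and changes no steroid management.

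1. State that the steroid condition for PD is judged over the two weeks before the MRI, the window the exception already uses. Growth above 25% with a decrease more than two weeks earlier is then PD, subject to Section 9.3.4, and never SD by default.
2. For scans made non-evaluable by a decrease within two weeks, state that PD is dated to the first scan if the next evaluable MRI still shows growth above 25% over the nadir, in line with Section 9.3.4.
3. State how a Month 12 scan made non-evaluable in this way is handled, since no later scan is scheduled.

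Making every scan after any decrease non-evaluable would be a poorer remedy. It would withhold PD even after a decrease 80 days old and could not resolve Month 12.

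The cost is a few sentences, with no added scans or patients. Expect slightly fewer SD calls and somewhat shorter reported PFS. Because Section 4.4 relies on Section 9 progression, check that the two sections still agree after the change.

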In a Phase IB study, six patients with recurrent, resectable malignant glioma were enrolled at the University of Alabama at Birmingham, in a trial examining a split dose administration strategy of G207 [15]. Patients underwent stereotactic inoculation of G207 into their tumors, followed two to five days later by resection of the tumor and reinoculation of G207 into the tumor cavity. 1×10^8 pfu was inoculated initially, followed by a second dose of 1×10^9 pfu. No dose limiting toxicities were seen in the trial, although one patient suffered a twelve hour period of mental status changes, contralateral paresis, and an elevated temperature when a protocol deviation resulted in an inadvertent partial dose of virus being administered intraventricularly. The patient fully recovered quickly. One of the six patients went nearly two years before remote recurrence of her *glioblastoma multiforme* resulted in her death.

A third study in 9 patients with recurrent malignant glioma was recently completed in which G207 was being administered followed by a single dose of 5Gy of radiation. Nine patients were followed without any dose limiting toxicity. Results of this trial are pending completion of a manuscript for submission for publication.

In a phase 1 study utilizing a similar oncolytic HSV vector, nine patients with relapsed malignant glioma received intratumoral inoculation of 1716. Although 1716 carries only a deletion of the $\gamma_134.5$ gene (it does not carry the additional mutation of the U_L39 gene found in G207), it also caused no dose-limiting toxicity at all doses tested (maximum dose, 10^5 pfu) [16]. Both the G207 and 1716 studies used modified HSV strains that retained the tk gene, thus allowing potential response to standard anti-viral therapy if encephalitis occurred. Two additional studies of 1716 have been published, neither of which demonstrated any dose limiting toxicities [17-18].

M002 – a murine interleukin-12 expressing $\Delta\gamma_134.5$ HSV

[figure not shown]

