9.1.3 Target Lesions

All intracranial lesions that are likely manifestations of the patient's malignancy will be considered target lesions.

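### Response and progression are scored only on the treated tumor, so read literally a new untreated remote lesion is SD, PR or even CR, which conflicts with the plan's own definition of target lesions

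*Combined protocol and SAP*

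**What the plan says.** Section 9.1.3 states that all intracranial lesions likely to be manifestations of the malignancy "will be considered target lesions". Section 9.3.2 drops any assessment of non-target lesions for that reason.

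Section 9.3.1, headed as the evaluation of target lesions, uses a narrower object:

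- CR: "Disappearance of all treated enhancing tumor on MRI scan, off steroids, and neurologically stable or improved".
- PR: "greater than 50% reduction in the treated enhancing tumor on MRI scan, stable or reduced steroid dose, and neurologically stable or improved".
- PD: "greater than 25 % increase in the treated enhancing tumor on MRI scan, stable or increased steroid dose, and neurologically stable or worse".
- The remainder: "Stable Disease (SD) - all other situations".

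The same section ends with a note that, because this is considered an immunotherapy trial, "the appearance of lesion(s) does not necessarily indicate PD".

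Section 9.3.4 handles suspected pseudoprogression. It applies when tumor appears to enlarge or to enhance more in a way consistent with PD, calls for repeat assessment at 3 months, and dates true progression to the first scan that met the PD definition given earlier. It also has a separate route to progression through significant neurologic deterioration. Section 9.5 names PFS as a secondary endpoint without defining the event. Section 11.4.2 reports the percentages in CR, PR, SD and PD by cohort and overall.

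**The concern.** M032 is given as one infusion into a defined tumor region (Section 4.4), and Section 3.2.5 excludes actively growing multifocal disease at entry. A lesion that appears later at another site is therefore outside the treated tumor, and criteria tied to the treated tumor do not see it. The section that should assess all target lesions assesses a subset. Section 9.3.2 removes the category in which the others might have been recorded, and the SD remainder absorbs whatever is left.

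The outputs at stake are the trial's preliminary evidence of benefit: PFS (Sections 1.3 and 9.5) and the response percentages (11.4.2). The error has one direction, since leaving out a type of progression can only lengthen PFS and lower the PD percentage. Section 4.1.1 also allows increased PFS or OS to factor into the phase II dose choice if no MTD is reached, so the figures may be used for more than description. Section 4.4 ties efficacy follow-up and the acceptability of other glioma treatments to progression as defined in Section 9, so the gap reaches that section as well.

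**Working it through.** The plan states no figure for this point (no response rate, no PFS assumption, no share of remote progression), so there is none to reproduce. The check has two parts.

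**1. Literal classification.** Apply the four definitions of 9.3.1 to patients who all have a new enhancing lesion away from the treated site:

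| Treated enhancing tumor | Steroids | Neurology | Class under 9.3.1 |
|---|---|---|---|
| unchanged | stable | stable | SD |
| down 60% | stable | stable | PR |
| gone | off | stable | CR |
| up 20% | increased | worse | SD |
| up 30% | stable | stable | PD |

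The new lesion plays no part in any row; PD arises only when the treated tumor itself grows by more than 25%. Two limits apply. In the fourth row, 9.3.4 might override SD on neurologic grounds, and a steroid increase within two weeks of the scan brings the non-evaluable rule of 9.3.1 into play. The PR and CR rows need confirmation on the next scheduled MRI (9.4.1), but that repeats the same measurement.

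The other sections do not clearly change the result. The note in 9.3.1 implies that some new lesions are PD but gives no rule. Section 9.3.4 does not name new lesions, and its dating rule leads back to 9.3.1. Sections 9.3.3 and 9.4.2 mention recurrence without defining it.

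**2. Size.** The synopsis gives 8 to 24 patients. One misclassified patient moves the non-PD percentage by 100/N:

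- N=8: 100/8 = 12.5 points
- N=24: 100/24 = 4.2 points

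The effect on PFS needs the share f of PFS events that are a new remote lesion first, which the documents do not give. As an illustration only, assume exponential PFS with independent hazards and f between 5% and 30%. Ignoring those events multiplies the median by 1/(1−f):

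- f=5%: 1/0.95 = 1.05
- f=10%: 1/0.90 = 1.11
- f=20%: 1/0.80 = 1.25
- f=30%: 1/0.70 = 1.43

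These are upper-end values, because a remote lesion may soon be followed by local growth, neurologic progression or death, each of which could still end PFS.

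**The case against.** The strongest reply is that the plan did consider new lesions. Saying that their appearance does not necessarily mean PD implies that sometimes it does. The trigger in 9.3.4 speaks of tumor rather than treated tumor, and it allows progression to be declared when imaging changes or symptoms progress despite steroids. Its neurologic route is independent of lesion site. An assessor could use these to call a confirmed remote lesion progression.

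This stands in part. A reader might infer from the table that every remote progression would be missed; the text does not support that, because judgment and the neurologic route would catch some. But 9.3.4 returns to the PD definition of 9.3.1, so an assessor who follows the words and one who follows the intent would class the same scan differently.

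Other inferences also go too far:

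- That scans called non-evaluable in 9.3.1 fall into SD. The specific rule there takes them out of the residual class.
- That growth above 25% with improved neurology is part of the same error. The PD definition sets a neurologic condition on purpose; that is a choice of criterion, not a contradiction with 9.1.3.
- That a patient in the earlier split-dose G207 study (Section 2.1), who went "nearly two years before remote recurrence of her" tumor, would not have progressed under these criteria. Section 2.1 says nothing about her treated site, and scheduled MRIs here end at Month 12. The case shows that remote recurrence occurs; it gives no rate.
- That a disease-control rate is inflated. The plan names no such endpoint.

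It is also fair to say that these are descriptive secondary results from a small, non-randomized phase 1 trial.

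**Conclusion.** The point holds as a contradiction between 9.1.3 and 9.3.2 on one side and 9.3.1 on the other, with no imaging rule that clearly makes a confirmed new lesion PD. The direction of bias is certain: longer PFS and a lower PD percentage. The size cannot be derived from the documents. The firm arithmetic is the effect per misclassified patient, 12.5 points at the smallest planned N and 4.2 at the largest; the PFS multipliers rest on an assumed remote-first share and simple hazards.

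A reader might infer that the trial's main conclusion is at risk. It is not: the DLT/MTD primary endpoint does not use these criteria. The consequence beyond description is conditional, through the provision in 4.1.1 for choosing a phase II dose when no MTD is reached. The point should be corrected before the secondary endpoints are analysed.

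**What to change.** For endpoint classification:

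- In 9.3.1, replace the treated enhancing tumor with the target lesions of 9.1.3 in the CR, PR and PD definitions.
- State in 9.3.1 and 9.3.4 that a new lesion counts as PD once the repeat imaging of 9.3.4 confirms it, dated to the first scan that showed it. This keeps the allowance for pseudoprogression and follows the dating rule already in 9.3.4. A separate rule is needed because a small new lesion may not raise the combined measurement by more than 25%.
- Do not assign CR while any other enhancing tumor lesion is present.
- State in 9.5 that PFS uses this definition.

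Because 4.4 links follow-up and the acceptability of other treatments to progression as defined in Section 9, the sponsor must reconcile that section with the revised wording; how it does so is a clinical matter outside this point.

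The cost is a wording amendment and a re-read of scans already taken, so that all patients are classed alike. The documents do not state the anatomical coverage of the MRIs (footnote 5 of the study calendar leaves them to the Principal Investigator), so it should be confirmed that the scans allow this. Reported PFS and the SD and CR percentages may become less favourable.
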